## **STUDY MEDICATION: VORTIOXETINE**

Participants receiving vortioxetine will be provided 10 mg/day on days 1–14 of the treatment period, with the option to increase to vortioxetine 20 mg/day at the end of Week 2 based on investigator judgment. For the remaining 6 weeks, the dose of vortioxetine will be flexible at 10 or 20 mg/day as adjudicated by a research clinician.

## **Side effects**

Most Common:

- Gastrointestinal adverse events; including nausea, vomiting, constipation/diarrhea. Highest incidence occurs during the first week of treatment. 21-32%
- Sexual dysfunction 14-34%

Less Common: 1-10%

- Dry mouth
- Dyspepsia (discomfort of the abdomen)
- Dizziness
- Somnolence/sedation
- Fatigue
- Insomnia
- Abnormal dreams
- Hyperhidrosis (increase sweating)
- Arthralgia (joint pain)
- Decreased appetite

Rare: %10>

- Nervous system disorders
  - Skin and subcutaneous tissue disorders
  - Psychiatric disorders
- 
- Serotonin Syndrome has been reported with serotonergic anti-depressants (SSRIs, SNRIs, and others), including with Vortioxetine both when taken alone, but especially when coadministered with other serotonergic agents (including triptans, tricyclic antidepressants, fentanyl, lithium, tramadol, tryptophan, buspirone, and St. John's Wort).
  - Treatment with serotonergic antidepressants (SSRIs, SNRIs, and others) may increase the risk of abnormal bleeding. Patients should be cautioned about the increased risk of bleeding when Vortioxetine is coadministered with nonsteroidal anti-inflammatory drugs (NSAIDs), aspirin, or other drugs that affect coagulation.
  - Activation of Mania/Hypomania can occur with antidepressant treatment.
  - Angle Closure Glaucoma: Angle closure glaucoma has occurred in patients with untreated anatomically narrow angles treated with antidepressants.
  - Hyponatremia can occur in association with the syndrome of inappropriate antidiuretic hormone secretion (SIADH).

Please see product monograph for full details.

## Contraindications

Hypersensitivity to vortioxetine or any components of the formulation. Angioedema has been reported in patients treated with vortioxetine. The use of monoamine oxidase inhibitors (MAOI) intended to treat psychiatric disorders with vortioxetine or within 21 days of stopping treatment with vortioxetine is contraindicated because of an increased risk of serotonin syndrome. The use of vortioxetine within 14 days of stopping an MAOI intended to treat psychiatric disorders is also contraindicated.

Starting vortioxetine in a patient who is being treated with MAOIs such as linezolid or intravenous methylene blue is also contraindicated because of an increased risk of serotonin

syndrome.

## **Storage**

Medication will be stored at room temperature and locked at a medical health care facility.

## **Rationale for Vortioxetine**

It has been amply documented that vortioxetine has a beneficial effect on cognitive domains commonly reported to be negatively affected in MDD (i.e., executive function, attention/speed of processing, and memory) at a dose of 10-20 mg per day [10,19–21]. Moreover, vortioxetine is the only psychopharmacological agent currently available that has a regulatory label in the EU and many other countries in the world describing its benefit on cognitive dysfunction in patients with MDD [22].

## **Transition to Standard of Care**

Patients will be informed of the transition to standard of care procedures (outlined here) post study prior to providing consent to participate in the study. These procedures will also be outlined in writing in the patient consent form itself.

Upon completing the 8-week course of vortioxetine, if patients benefit from this drug, they will be encouraged to continue the treatment with their most responsible physician (MRP). Patients will be notified prior to study consent that not all drug plans will cover the cost of vortioxetine. Should patients wish to continue to use this drug post-study when they do not have coverage, they will be personally responsible for the costs. There will be a gradual discontinuation of the medication for two weeks after the end of the study. However, participants will not have further access to this drug from the research team after study completion. If patients do experience side effects during the study, a physician will make a recommendation regarding the discontinuation or dose reduction of the medication for the remainder of the study. If patients do not experience

any improvement upon study completion in mood or cognition, the medication will be gradually discontinued over a two-week period upon study completion (week 8).

## **Vortioxetine discontinuation process**

At visit 8, patients will be seen by a clinician and provided with half of current vortioxetine dosage for a period of 1 week. This down titration will assure there are no adverse side effects with discontinuation of vortioxetine. During the second week, patients will not be on medication and will be seen by the clinician at the end of two weeks, to ensure that there are no risks or adverse events during this time period. The visits with the clinician are post-study, and not part of the study visits. Patients are encouraged to contact the 24/7 study phone line in the event that they would like to be scheduled with the physician earlier. MDD patients will be seen by research clinician to ensure a safe transition into standard of care by their main responsible physician.

## **CONDITIONS FOR WITHDRAWAL FROM THE STUDY**

Participants may discontinue from the study treatment and assessments at any time. Specific reasons for discontinuing a participant from this study are:

1. Voluntary discontinuation by the participant at any time without prejudice to further treatment.
2. Non-compliance to the protocol as judged by the investigator.
3. Participant becomes pregnant.
4. Increased risk of suicide ideation.
5. Any adverse event that, in the opinion of an investigator, puts the subject at risk.

## RECRUITMENT

Membership of the BCDF provide consultation to approximately 20 new adult MDD patients per week. It is expected that approximately 10 participants per month will be eligible for the study herein. This estimate is based on previous experience in which a high proportion of persons referred to the THINC-it validation study met inclusion criteria. The clinical research experience of BCDF members demonstrates that it is possible (as evinced by publications) to recruit a minimum of two subjects per week for most studies conducted. Recruitment of all eligible subjects will be via media announcements in the general community. It is anticipated that the attrition rate will be 20%. Healthy controls will be consecutively recruited via media announcements and will be age-, sex- and education-matched in a 2-to-1 ratio.

The loss to follow-up rate in our program has been relatively low, based on previous experience. The estimated dropout rate in our experience has been approximately 20% for open-label studies. With this in mind, however, the present study has been sufficiently powered to achieve the primary aims and objectives.

## STATISTICAL PLAN

Extant literature indicates that the effect size for cognitive deficits in first- and multiple-episode MDD patients is approximately 0.3-0.7 (Cohen's *d*). Notwithstanding the range of reported effect sizes, a modal estimate of 0.4 is instantiated by meta-analyses across disparate domains [23]. Based on an effect size of 0.4, it is estimated that a sample size of 110 evaluable subjects would be required (with a power level of 0.8 and a probability level of 0.05). Similarly, results from our recently completed validation study of the THINC-it demonstrated- temporal reliability of 0.7-0.8, suggesting that repeat-measure performance on the THINC-it between visits would be consistent in the study being proposed herein. Taken together, performance on all the THINC-it tool metrics will be collected in the healthy control group (N=50) for comparison with performance of patients with MDD treated with vortioxetine over an 8-week period, flexibly dosed 10-20 mg/day as adjudicated by a research clinician, to assess detectable differences between groups.

Participants with complete data from the 8 weeks of treatment will be included in analyses, which will be carried out using the Statistical Package for the Social Sciences (SPSS) software. The data will be preliminarily examined in exploratory analyses to obtain their distributional properties, examine any outlying data points, and explore bivariate relations between individual variables. Specific data analyses are subject to change based on the foregoing analyses, but in general we will set  $\alpha = 0.05$ , two-tailed, and  $\beta = 0.20$ .

Validation assessments will be employed based on previous psychometric validations of cognitive assessment, as reported by Harrison et al. (2007) wherein validation was informed by guidance regarding objective psychometric assessment by Ferris et al. (1997) stressing the importance of characterizing the reliability, validity, and sensitivity of cognitive measures; in addition, results from a recently completed validation study of the THINC-it completed by the BCDF will be used to determine the appropriate statistical measures required to perform the study herein.

An important consideration when determining issues such as temporal (or 'test-retest') reliability

is a reasonable expectation that the performance will not be impacted by disease or medication variables. Hence, it is necessary to conduct these analyses in a group of healthy controls (N=50) as compared to an intervention group (N=100) assessing sensitivity to change during vortioxetine treatment flexibly dosed 10-20 mg/day over an 8-week period.

Evidence to date indicates that average performance on cognitive tasks in patients with MDD fall approximately 0.5-1.0 standard deviations (SD) below healthy control normative data that is age, sex and education matched [17]. In this study, a comparison of performance in the healthy control group versus the treatment group with vortioxetine over an 8-week period, flexibly dosed 10-20 mg/day, will demonstrate both the deficit of magnitude as well as margin of improvement following 8 weeks of vortioxetine treatment in the latter group. Data from both groups will allow a comparison of overall THINC-it performance as well as improvement following vortioxetine treatment (sensitivity and specificity) on each test comprising the THINC-it tool.

Interim analysis will be conducted both at primary and secondary measures.

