## **RATIONALE FOR SECONDARY ASSESSMENTS INSTRUMENTS**

A critical question for addressing cognitive impairments in adults with MDD is not whether it exists, but rather determining whether these observed impairments in cognitive function/performance influence patient-reported, clinician-measured, and/or societally defined health outcomes. The answer to which additional testable hypotheses can be generated is to further investigate to what extent cognitive impairments affect these health outcomes and what methods of treatment are available to mitigate these cognitive symptoms. The pen and paper version of the DSST and PDQ-5-D will be administered as an additional measure of validity. Additionally, most individuals achieving remission continue to report/exhibit ongoing functional difficulties as well as significant reductions in quality of life, providing impetus for their measurement [14,15]. Consequently, the WHO-5 will be administered to assess overall quality of life and wellbeing.

Moreover, these deficiencies correlate with greater illness burden measures and costs, particularly in the workplace [16]. Likewise, it is recognized that cognitive function in adults with MDD represents a principal determinant of broad-based psychosocial function [15,17,18]. Taken together, the SDS and EWPS will be administered to allow for secondary evaluation of the relationship between global functional impairment/disability and health-related work productivity with cognitive function in adults with MDD, respectively. It has been amply documented that impairments in cognitive function are correlated with, but dissociable from, depressive symptom severity [18]. Hence, the relationship between measures of cognitive impairment and depressive symptoms severity will include the following secondary measures: the MADRS, the CGI-S/CGI-I, and the CSSRS.

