### ***Visit 3 (Day 14; Week 2)***

Participant will be asked to report any adverse event(s) or any changes to medications. The Clinical Global Impression – Severity (CGI-S), Clinical Global Impression – Improvement

(CGI-I), MADRS, as well as the CSSRS scales will be used as part of participant assessment. History of caffeine, alcohol, nicotine, and marijuana use will be recorded. Anthropometrics (including weight and waist circumference), resting heart rate and blood pressure data will be measured as well. THINC-it tool will be administered via tablet to evaluate objective and subjective measures of cognitive function. THINC-it tests will be consistently delivered in the following order: Spotter, Symbol Check, Codebreaker, Trails, and PDQ-5-D to all participants with a member of the research team instructing participants to read the tutorial instructions preceding each of the THINC-it tasks. Participants will complete the pen-and-paper version of the Digit Symbol Substitution Test (DSST) and the Trail Making Test B (TMT-B).

Participants will also complete all secondary self-report assessments using paper-based scales/questionnaires and consist of the following scales: Endicott Workplace Productivity Scale (EWPS), Sheehan Disability Scale (SDS), Wellbeing Index (WHO-5), Snaith-Hamilton Pleasure Scale (SHAPS), Generalized Anxiety Disorder (GAD-7), Perceived Deficits Questionnaire for Depression (PDQ-5-D), 36-Item Short Form Survey Instrument (SF-36), Insomnia Severity Index (ISI), Pittsburgh Sleep Quality Index (PSQI), Epworth Sleepiness Scale (ESS) and THINC-it satisfaction questionnaire. All self reports will be administered by a member. All study procedures will take place in a quiet setting.

Participants will receive vortioxetine 10-20 mg (flexibly dosed) over the next 2 weeks to be taken once daily with the option to increase to vortioxetine 20 mg/day based on clinical discretion (e.g. efficacy and tolerability). This dose was chosen based on extant evidence demonstrating improvements in cognitive function (i.e., executive function, attention/speed of processing, and memory), independent of improvement in depressive symptoms, over an 8-week period [19, 20]. Participants will be asked to store the medication at room temperature (i.e., 15-30 °C).

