***Visit 4 (Day 28; Week 4)***

A member of the research team will complete the MADRS, CGI-I, CGI-S, IPAQ and CSSRS with the participant as well as ask about any side-effects or changes to their medications. History of caffeine, alcohol, nicotine, and marijuana use will be recorded. Anthropometrics (including weight and waist circumference), resting heart rate and blood pressure data will be measured as well. Participants will receive additional vortioxetine for the following 4 weeks.

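### Analyses are limited to participants with complete 8-week data although 20% attrition is expected, with no missing-data method, second analysis set or sensitivity analysis

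*Combined protocol and SAP*

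**What the plan says.** The STATISTICAL PLAN sets one analysis rule: "Participants with complete data from the 8 weeks of treatment will be included in analyses". It does not define complete data, which could mean every visit and scale or only the THINC-it values being analysed. The reference to treatment does not fit the untreated controls.

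RECRUITMENT says "It is anticipated that the attrition rate will be 20" per cent, and its only response is "With this in mind, however, the present study has been sufficiently powered to achieve the primary aims and objectives". The STATISTICAL PLAN estimates that "a sample size of 110 evaluable subjects would be required" without saying whether this counts both groups or MDD patients only. It also lets specific analyses change after exploratory checks, but that clause names no way of handling missing values. No section gives imputation, a repeated-measures model, another analysis set or a missing-data sensitivity analysis.

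THINC-it is scheduled at Weeks 0, 2 and 8 (MDD PATIENT SUMMARY CHART). At Week 2, "THINC-it tool will be administered via tablet to evaluate objective and subjective measures of cognitive function". At Week 4, "A member of the research team will complete the MADRS, CGI-I, CGI-S, IPAQ and CSSRS with the participant", with no THINC-it. CONDITIONS FOR WITHDRAWAL FROM THE STUDY lets participants stop assessments as well as treatment. Its listed reasons include non-compliance, increased risk of suicide ideation, and "Any adverse event that, in the opinion of an investigator, puts the subject at risk".

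**The concern.** The primary objective is how sensitive THINC-it is to change over 8 weeks, and Test Sensitivity reports group differences as standardised effect sizes. The size of the change is therefore itself a main result. Under the stated rule it describes completers only.

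Some listed withdrawal reasons could be related to outcome. Vortioxetine adverse events can remove MDD patients but not controls, which bears on the between-group contrast. RECRUITMENT answers attrition with a statement about power, which does not address selection.

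The rule also sets aside data already collected: the baseline data of everyone who leaves, the Week 2 THINC-it and MADRS of those who leave after Week 2, and the Week 4 MADRS of later leavers. Week 2 THINC-it change is the predictor in both secondary objectives, so those analyses are confined to completers too.

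**Working it through.** **Inputs from the document.** 100 MDD patients and 50 controls (STUDY POPULATION); 20% attrition (RECRUITMENT); d = 0.4, power 0.80, two-tailed alpha 0.05, 110 evaluable subjects, temporal reliability 0.7-0.8 (STATISTICAL PLAN).

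**Assumptions.** Controls leave at the same 20%. True MDD change is 0.20 SD at Week 2 and 0.40 SD at Week 8 (the plan's 0.4 is a deficit effect size, not a change). Correlation between any two visits is 0.75, guided by the stated reliability. Dropout is 20%, after Week 2, with log-odds slopes from -1 to +1 per SD of change.

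1. **The plan's 110.** With (1.960 + 0.842)² = 7.85:
   - two groups 1:1: 2 × 7.85 / 0.16 = 98.1, so 99 per group, 198 in total;
   - 2:1: 1.5 × 7.85 / 0.16 = 73.6, so 74 controls, 222 in total;
   - one group, standardised change 0.4: 7.85 / 0.16 = 49.1, so 50.

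   None gives 110. A 2:1 change-score comparison at correlation 0.75 gives 111, but the plan states neither that test nor that correlation. This is a separate matter and nothing below depends on it.

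2. **Numbers analysed.** 0.8 × 100 = 80 MDD; 0.8 × 50 = 40 controls; total 120.

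3. **Precision.** The interval for within-MDD change widens by √(100/80) = 1.118, about 12%. For two groups at d = 0.4:
   - 100:50: SE = √(1/100 + 1/50) = 0.173; power about 63% (t-based; 64% by normal approximation);
   - 80:40: SE = √(1/80 + 1/40) = 0.194; power about 54%.

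   For the baseline comparison with controls, everyone has a Week 0 value, so the whole fall comes from the rule. At Week 8 the dropouts' values are missing under any analysis, so 63% is a ceiling there. Power for a within-MDD standardised change of 0.4 is about 94% with 80 against 98% with 100.

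4. **Bias formula.** Completer bias = dropout fraction × (completer mean change − dropout mean change). At 20% dropout, an assumed gap of 0.2 to 0.5 SD either way gives 0.04 to 0.10 SD in that direction. A zero gap gives none.

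5. **Simulation of Week 8 change (true value 0.40 SD).**

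| Dropout depends on | Completers | Model using all Week 0, 2 and 8 values |
|---|---|---|
| Nothing | 0.40 | 0.40 |
| Week 2 change | 0.34-0.46 | 0.40 |
| Unseen Week 8 change | 0.28-0.52 | 0.31-0.49 |

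   Check with the formula: if completers average 0.46, dropouts average (0.40 − 0.8 × 0.46) / 0.2 = 0.16, and 0.2 × (0.46 − 0.16) = 0.06. The standard error with 80 patients is √(2 × 0.25) / √80 = 0.079. The Week 2-driven shift of 0.06 is therefore below one standard error but is 0.06 / 0.40 = 15% of the change. The Week 8-driven shift of 0.12 is about 1.5 standard errors.

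6. **Varying the assumptions (Week 2-driven).**
   - Correlation 0.7-0.8: completers 0.33-0.47. Correlation 0.5: 0.31-0.49. The model stays at 0.40.
   - If a quarter to a half of dropouts have no Week 2 data, the model gives 0.38-0.42. If all leave before Week 2, it gives about 0.35-0.45 against 0.34-0.46 for completers, recovering about a quarter of the bias before rounding.
   - MDD-minus-control contrast, assumed true value 0.20 (practice change 0.20 SD and random 20% dropout in controls): completers 0.14-0.26, model 0.20.

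**The case against.** The strongest reply is that the target is arguable. For a question about an instrument's responsiveness, change among people who received 8 weeks of treatment is defensible, and completers estimate it. That stands as far as it goes, but the plan does not name this target. The bias described here is bias for mean change in all enrolled patients.

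Second, no link between dropout and THINC-it change is shown. The withdrawal reasons do not mention cognition, and the rationale section holds that "impairments in cognitive function are correlated with, but dissociable from, depressive symptom severity". If dropout is unrelated to change, completers are unbiased. This also stands, and it is why no direction can be claimed.

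Third, the remedy is limited. Side effects says gastrointestinal events peak in the first week, so some patients may leave before the Week 2 test. If dropout depends on unseen Week 8 change, only about a quarter of the bias is removed. Multiple imputation could serve as well as a mixed model. These points limit the gain but do not defend the present rule.

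Three stronger readings are tempting, and the documents support none of them:
- A reader might infer that the rule inflates the effect. Nothing in the documents fixes the direction.
- A reader might infer that precision is safe because 120 exceeds 110. That holds only if 110 is a total; if it means MDD patients, the expected 80 fall short.
- A reader might infer that every dropout's Week 2 data are lost. Only those who leave after Week 2 have such data, and dropout timing is not given.

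**Conclusion.** The point holds. The plan states a completers-only rule, expects one in five to leave, and has no analysis that would show whether the completer result is too large or too small for all enrolled patients.

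Under the stated assumptions the shift is up to 0.06 SD either way on 0.40 if dropout follows Week 2 change, and up to 0.12 SD if it follows unseen Week 8 change. These are illustrations, not estimates for this trial. The smaller shift is below one standard error, so it affects the reported effect size more than the within-group test. The precision cost comes on top of any bias.

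This is a cheap improvement. The documents do not support saying that the primary result would be invalid.

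**What to change.** Replace the rule in the STATISTICAL PLAN as follows:

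- State the target: mean THINC-it change over 8 weeks in all enrolled MDD patients, and its contrast with controls.
- For the primary metric of each THINC-it test, include every MDD participant and control with a baseline value in a likelihood-based repeated-measures model with group, visit and group-by-visit terms, using all available Week 0, 2 and 8 values.
- Keep completers as a sensitivity analysis, defined as those with both Week 0 and Week 8 THINC-it.
- Report dropout by visit, group and reason.
- Add one sensitivity analysis that assumes worse unseen Week 8 values in dropouts. With 20% dropout, each 0.1 SD worse lowers mean change by 0.20 × 0.1 = 0.02 SD.

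The cost is SAP wording and minor analysis work, with no new visits or data. The estimate may be less favourable. Residual bias remains if dropout depends on unseen Week 8 values, and the gain is smaller if many leave before Week 2.

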## OBJECTIVES

### *Primary Objective:*

❑ To determine the sensitivity of the THINC-it to alterations in cognitive function/performance following intervention with vortioxetine over 8 weeks in adults aged 18-65 with MDD.

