## Test Sensitivity

Performance on the primary metric for each THINC-it tool test will be calculated to determine test sensitivity. Descriptive statistics for performance of i) the Healthy Control group and ii) that of the patients with MDD treated with vortioxetine over 8 weeks will be examined to determine:

- Mean difference in performance on each test
- Variance in performance for each test
- Additional measure of central tendency and variability
- Other descriptions of the data, including skewness and kurtosis
- Mean difference in group performance, characterised as a standardised effect size

Inferential statistical analysis will be conducted to determine significant difference in

performance within and between the two groups. An analysis of the sensitivity (true positive rate) and specificity (the true negative rate) of each test to the presence and subsequent improvement of cognitive impairment in patients with MDD will be conducted. Cut-off models designed to maximize sensitivity and specificity will be evaluated. The model will be optimized to obtain a pragmatic cut-off that maximizes the model with respect to levels of both sensitivity and specificity. In the event that no overlap is apparent, a threshold for determining impairment will be established. Secondary objectives will be addressed with correlative analysis between the total THINC-it tool and/or its components and the disparate secondary measures.

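### The plan intends to compare improvement with healthy controls, but commits to no test of MDD-minus-control change on the THINC-it and no multiplicity rule; separately, its optimised cut-offs have no validation step

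*Combined protocol and SAP*

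**What the plan says.** The primary objective is "To determine the sensitivity of the THINC-it to alterations in cognitive function/performance following intervention with vortioxetine over 8 weeks". Both summary charts schedule the THINC-it at Weeks 0, 2 and 8, so the same change can be computed in MDD participants and controls.

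The Statistical Plan describes "healthy controls (N=50) as compared to an intervention group (N=100) assessing sensitivity to change" and then says "Data from both groups will allow a comparison of overall THINC-it performance as well as improvement following vortioxetine treatment". In the same paragraph the improvement is located in the MDD group only: "margin of improvement following 8 weeks of vortioxetine treatment in the latter group".

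Test Sensitivity sets the outcome: "Performance on the primary metric for each THINC-it tool test will be calculated to determine test sensitivity". It lists descriptive summaries, including "Mean difference in group performance, characterised as a standardised effect size", and promises inferential analysis of "performance within and between the two groups". It names no test or model, does not say whether the between-group comparison uses baseline, Week 8 or change, and gives no rule for multiple tests. The Statistical Plan also lets analyses be altered after the data have been explored.

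On cut-offs, Test Sensitivity says: "The model will be optimized to obtain a pragmatic cut-off that maximizes the model with respect to levels of both sensitivity and specificity". No hold-out sample, resampling or external check is described. The validation work mentioned in the Statistical Plan concerns the psychometric properties of the tool, not these cut-offs.

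**The concern.** People often score better on a cognitive task the second or third time they take it. Without a control series, a gain in treated patients mixes practice with real change. This trial has such a series, but the text does not bind the analyst to use it for change. A within-MDD test of baseline to Week 8, plus a test of group levels at one visit, would satisfy the wording. The first includes the practice gain. The second measures a deficit, not a change.

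The intermediate shortcut is also weak. Finding a significant gain in MDD and none in the smaller control group is not evidence that the gains differ, because the control test has about half the sample. At stake is the primary claim: the THINC-it could be reported as sensitive to change when both groups improved equally through repetition. The argument applies to the four objective tests; the PDQ-5-D is self-report.

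The cut-off issue is separate and lesser. Sensitivity and specificity taken from the data used to choose the threshold will be optimistic.

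**Working it through.** **The plan's sample size.** The Statistical Plan gives 110 evaluable subjects for an effect of 0.4, power 0.8 and level 0.05, without naming the test. With (1.960 + 0.842)²/0.4² = 49.1, a paired test needs 50 subjects, a 1:1 two-group test 2 × 99 = 198, and a 2:1 two-group test 74 + 148 = 222. None gives 110, so the figure does not reveal which test was intended. The 0.4 is described as a cognitive deficit, not a change. I use 110 for nothing below.

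**Inputs from the documents.** 100 MDD and 50 controls; 20% attrition (Recruitment), applied here to both groups, and complete-data analysis, giving 80 and 40; temporal reliability r = 0.7 to 0.8; two-sided 0.05 (Statistical Plan).

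**Assumptions.** Practice gain g of 0.1 to 0.3 baseline SD, equal in both groups; no treatment effect; equal SDs. SD of change = √(2(1 − r)) = 0.775 at r = 0.7 and 0.632 at r = 0.8.

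**Practice only.** The one-sample t-test has noncentrality g√n / SD of change; for g = 0.2, r = 0.7, n = 80 this is 0.2 × 8.944/0.775 = 2.31. The joint result is P(MDD significant) × (1 − P(control significant)). Each cell shows r = 0.7 / r = 0.8.

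| g (SD) | MDD significant, n = 80 | Control significant, n = 40 | MDD yes, control no |
|---|---|---|---|
| 0.1 | 0.207 / 0.287 | 0.125 / 0.164 | 0.181 / 0.240 |
| 0.2 | 0.626 / 0.798 | 0.357 / 0.496 | 0.403 / 0.402 |
| 0.3 | 0.928 / 0.987 | 0.666 / 0.833 | 0.310 / 0.165 |

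If all 50 controls complete, the last column becomes 0.177 / 0.231, 0.355 / 0.326 and 0.217 / 0.091. If reliability were 0.5 (an assumption outside the stated range), g = 0.2 gives 0.424 within MDD and 0.424 × (1 − 0.235) = 0.324 jointly.

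**Test of difference in change.** With equal practice its expectation is zero whatever g is. Simulated rejection was 0.049 to 0.052 in every setting.

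**Multiplicity.** Unadjusted on four independent tests, the chance of at least one false positive is 1 − 0.95⁴ = 18.5%. In simulation it was 13% to 19% for change-score correlations of 0.7 down to 0.

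**Power of the contrast, 80 v 40.** SE = SD of change × √(1/80 + 1/40) = 0.150 / 0.122 baseline SD.

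- Net gain 0.4 baseline SD: 0.753 / 0.900.
- Net gain 0.2: 0.262 / 0.367; at Holm's first step (0.05/4 = 0.0125), 0.119 / 0.188.
- If 0.4 means SD-of-change units: noncentrality 0.4/0.194 = 2.07, power about 0.54.
- 95% CI half-width: 0.297 / 0.243 baseline SD.

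**Unequal practice.** If MDD participants gain 0.1 SD more from practice than controls, the contrast rejects in 10% to 13% of trials; at 0.2 SD more, 26% to 37%.

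**Cut-offs.** Simulated normal scores, 80 v 40, cut-off chosen to maximise the Youden index (sensitivity + specificity − 1).

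| d | Apparent | True, new subjects | 10-fold cross-validated |
|---|---|---|---|
| 0.4 | 0.242 | 0.140 | 0.139 |
| 1.0 | 0.450 | 0.364 | 0.366 |

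This covers MDD-versus-control discrimination only, not cut-offs for improvement.

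**The case against.** The best defence is that the plan already covers this. It speaks of comparing improvement using both groups, promises inference within and between them, and collects the THINC-it at matching weeks. A mixed analysis with a group-by-time term is a natural reading. That stands. A reader might infer that the plan has chosen a wrong analysis or forgotten its controls; the documents do not support that. What they show is that the right analysis is permitted but not required.

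The sentence describing "healthy controls (N=50) as compared to an intervention group (N=100) assessing sensitivity to change" is weaker evidence than it looks. It follows a discussion of test-retest reliability, and the analyses it calls for in controls refer back to that. The intention to compare improvement rests better on the next paragraph, from which "Data from both groups will allow a comparison of overall THINC-it performance as well as improvement following vortioxetine treatment" comes.

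A reader might also take the within-MDD rates, up to 99%, as the plan's false-positive rate. They are not. The promised within-group inference includes controls, whose retest gain would expose shared practice unless ignored. The joint figure is nearer to the risk.

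It is tempting to say that the outcome score is undefined. The Background mentions a composite and the Statistical Plan refers to overall performance, but the analysis text points to one metric per test. The real gap is multiplicity.

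Finally, the baseline practice step in both charts may shrink the practice effect. Nothing in the plan measures what remains.

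**Conclusion.** The concern holds as one of under-specification affecting the primary claim, and should be fixed before analysis. Under equal practice of 0.1 to 0.3 SD, no treatment effect, r = 0.7 to 0.8 and 80 v 40 completers, reading sensitivity to change from MDD significant and controls not would mislead in about 17% to 40% of trials (9% to 36% with all 50 controls). The within-MDD test alone would be significant in 21% to 99%, which matters only if the control result is set aside. Practice size is assumed throughout.

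A reader might infer that the change contrast would isolate an effect of vortioxetine. It would not: the groups are not randomised, and only practice common to both is removed. Its 5% level depends on practice being equal.

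The cut-off point also holds, at lower severity: an optimism of about 0.10 in the Youden index at d = 0.4 and 0.09 at d = 1.0, under normal scores.

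**What to change.** 1. Prespecify the MDD-minus-control difference in change from baseline to Week 8 as the between-group test of sensitivity to change: a group-by-time contrast with 95% CI, from a longitudinal model that treats baseline as one of the outcomes. This suits non-randomised groups that the Statistical Plan expects to differ by 0.5 to 1.0 SD at the outset. Apply it to Spotter, Symbol Check, Codebreaker and Trails with Holm adjustment, or to one named composite with its formula. Report the PDQ-5-D separately.
2. Keep the within-MDD change as a result reported alongside, but do not rest the conclusion on it alone, or on significance in one group and not the other. State that the contrast does not remove natural recovery, regression to the mean (MDD participants are selected on MADRS), ceiling effects or differential practice.
3. Report cross-validated sensitivity and specificity, repeating the cut-off search in each fold.

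No new data are needed, but there is a cost in power that the plan should disclose. With 80 v 40, power is 75% to 90% for a net gain of 0.4 baseline SD, which is as large as the whole modal deficit the plan cites. It is 26% to 37% for 0.2 SD (12% to 19% at Holm's first step), and about 54% if 0.4 is in SD-of-change units. The scale should therefore be stated. Reported cut-off accuracy will look less favourable.
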